3.10.2.8 Tipping point analysis

If the primary analysis is statistically significant in favor of GMRx2, a MI tipping point analysis may be performed in the Randomized Population to assess the impact of missing data under the assumption that data are not missing at random. A two-dimensional tipping point analysis will be performed where the trajectories of participants in the GMRx2 treatment group with missing Week 12 data will be imputed separately from the trajectories from the active control treatment groups with missing Week 12 data. A shift parameter, delta, will be added to each imputed value. The three active control treatment group will be imputed with a shift of 0. The shift parameter applied to the GMRx2 treatment group will be applied across a range of values. Successively larger deltas will be imposed on the imputed values of GMRx2 treatment group until statistical significance is lost, i.e. two-sided p-value is >0.05 and no longer in favor of GMRx2 for at least one of the pairwise comparisons.

3.10.2.9 Descriptive figures

The following graphical displays are planned:

- Plot of the LS Mean home SBP with 95% CI derived from the MMRM for the primary analysis will be presented.
- Results from the tipping point analysis will be presented graphically.
- Forest plots of the LS Means, 95%Cl and p-values for determining heterogeneity by subgroup will be presented.
- Descriptive scatter plots to display the average weekly SBP post-randomization, where Week 1 begins at first treatment post-randomization, Week 2 begins at Day 8 of treatment post-randomization, etc.
- Descriptive scatter plots to display the change in average weekly SBP from randomization through the Randomization Period. Randomization will be defined as the 7 calendar days prior to the Randomization clinic visit (Table 3-3). The Randomization Period will begin on the first day of randomized treatment and will extend until the earliest of: Week 12 visit, End of Study visit, or 14

weeks of post-randomized BP home measurements.

• Descriptive scatter plots to display the change in average weekly SBP from end of Phase 2/FU1 visit through Period 3. End of Phase 2/FU1 visit will be defined as the 7 calendar days prior to the FU1 Week 6 clinic visit (Table 3-3). Period 3 will begin on the first day of treatment following FU1 Week 6 clinic visit and will extend until the earliest of: Week 12 visit, End of Study visit, or 7 weeks of Period 3 BP home measurements.

Scatter plots may be presented for the treatment groups overall as well as by subgroups, as appropriate. Similar plots may be presented for home DBP, as appropriate.

3.10.3 Analysis of Secondary Efficacy Outcomes

3.10.3.1 Home Blood Pressure

Analysis of home SBP and DBP secondary continuous endpoint analysis on change from baseline (randomization) will be performed on Complete Cases only, including all data available. Summary statistics, including number with missing observations, at each timepoint will be presented. Mixed models with repeated measures (MMRM) will be applied for continuous variables using the same approach as the primary endpoint (with no imputations applied).

- Difference in change in mean home SBP from randomization to Week 6,
- Difference in change in mean home DBP from randomization to Week 12,
- Difference in change in mean home DBP from randomization to Week 6,
- Difference in change in trough (i.e. before morning dose) home mean SBP from randomization to Week 12,
- Difference in change in trough (i.e. before morning dose) home mean SBP from randomization to follow-up Week 6

Additional exploratory analyses, including longitudinal models for all home SBP measurements collected during Week 6 and Week 12 may be performed.

Descriptive summaries of binary endpoints will include the number and percentage of participants with controlled BP, i.e.:

- weekly averaged SBP <135 and DBP <85 mmHg at Week 12,
- weekly averaged SBP <135 and DBP <85 mmHg at Week 6,
- weekly averaged SBP <130 and DBP <80 mmHg at Week 12,
- weekly averaged SBP <130 and DBP <80 mmHg at Week 6

Frequency of missing data will be reported.

Data will be summarized as reported, including only complete cases. Estimated proportions by treatment groups with exact Clopper-Pearson 95% CI will be presented along with the associated estimated risk difference, risk ratio, and corresponding p-values. The number and percentage with 95% CI of participants with controlled BP at Week 12 will be summarized by treatment group by:

- Number of prior therapies at enrolment
- Controlled or uncontrolled BP status at Randomization

Binary secondary endpoints will be analyzed using Generalized Estimating Equations (GEE) to account for repeated measures. For the regression analysis, participants with missing endpoint data (Week 6 or Week 12) will be imputed as "failure" at the respective timepoint(s). The GEE regression analyses will be performed on the Randomized Set. The outcome will be the post-Baseline occurrence of the event at Week 6 and Week 12 with fixed effects for treatment group, time (visit as categorical variable), treatment by time (visit) interaction,

and Baseline home SBP. The variance will be estimated using a sandwich estimator and the model to account for correlation within participant and within site. A compound symmetry covariance matrix will account for correlation within participant and site, with a fall back of an independent matrix if the model does not converge. The odds ratios and 95% CIs for the occurrence of the events will be estimated for each post-Baseline visit and treatment group. In addition, risk differences and 95% CI will be computed for each post-Baseline visit to evaluate pairwise differences between GMRx2 and dual treatments at Week 6 and Week 12.

Sample SAS Code:

```
PROC GENMOD DATA = ADEFF;
CLASS SITEID SUBJID VISIT TRTP;
MODEL AVAL = BASE VISIT TRTP VISIT*TRTP / DIST = BIN CL;
REPEATED SUBJECT = SUBJID(SITEID) / TYPE = EXCH;
WHERE VISIT IN ('WEEK6','WEEK12');
LSMEANS VISIT*TRTP / DIFF CL ALPHA=0.05;
RUN;
```

Risk differences and 95%CI for comparisons between the occurrence of events in GMRx2 group versus each dual control will be computed using the Predictive Margins and Average Marginal Effects SAS Macro (https://support.sas.com/kb/63/038.html). Sample SAS code with implementation to simulated data is provided in Appendix 4.

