12.4. Statistical Methods

All analyses will be performed on an intention-to-treat basis. Baseline characteristics by the group will be compared using descriptive analyses. The primary outcome of difference in change in home SBP from baseline to Week 12 will be analyzed using a mixed model for repeated measures with baseline BP, visit, treatment group, and visit by treatment group interaction as a fixed effect and accounting for correlation within participant and clustering at the site level. Other continuous outcomes of difference in change in BP will also be analyzed as the primary outcome. All continuous outcomes will be reported along with 95% CI and the corresponding p-value. The percentage of participants achieving target BP at Week 6 and Week 12 will be summarized descriptively and analyzed using generalized estimating equations with the visit, treatment group, and visit by treatment group interaction as a fixed effect and accounting for correlation within participant and clustering at the site level. Percentages by treatment groups with 95% CI will be presented along with the associated estimated odds ratio and its corresponding p-value. Other binary outcomes of efficacy and safety will be analyzed as the percentage of participants achieving target BP. The primary analysis dataset will be locked after the last participant has reached the 16 week follow-up visit.

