3.10.2.2 Main Analysis

Blood pressure values will be summarized using descriptive statistics, including actual values and changes from baseline to Week 6 and Week 12, by timepoint and treatment groups. Graphical presentations of group means over time will be presented. Summaries will be presented on the Safety Set by Randomization Status and Randomization Set. Additional summaries may be presented.

The difference in change of home SBP from Baseline to Week 12 will be analyzed using a MMRM. The outcome will be the post-Baseline home SBP values with fixed effects for treatment group, time (visit as categorical variable), treatment by time (visit) interaction, and Baseline home SBP. The variance will be estimated using a Huber-White sandwich estimator and the model will account for correlation within participant and within site. An unstructured covariance matrix for within participant observations will be used with fall-backs to first a compound symmetry (exchangeable) matrix and finally an independent matrix if the model does not converge. A compound symmetry covariance matrix will account for correlation within site with a fall back of an independent matrix if the model does not converge. Least Square Means and corresponding standard errors will be estimated for each post-Baseline visit and treatment group. Pairwise comparisons between GMRx2 and dual treatments will be performed at Week 6 and Week 12. The comparisons at Week 12 will serve as the

primary endpoints analysis.

```
Sample SAS Code:
    PROC MIXED DATA = ADEFF EMPIRICAL METHOD = REML;
    CLASS SITEID SUBJID VISIT TRTP;
    MODEL AVAL = BASE VISIT TRTP VISIT*TRTP / CL;
    REPEATED VISIT SUBJID / SUBJECT = SITEID TYPE = UN@CS;
    WHERE VISIT IN ('WEEK6','WEEK12');
    LSMEANS VISIT*TRTP / DIFF CL ALPHA=0.05;
    RUN;
```

Where ADEFF is the ADaM dataset for efficacy, AVAL represents the Week 6 or Week 12 home SBP measurement, BASE is the Baseline value, VISIT is the visit (Week 6 or Week 12), TRTP is the planned treatment, and VISIT*TRTP is the interaction between visit and planned treatment.

Superiority of the triple combination over the dual combinations will be shown if the 3 comparisons listed above are statistically significant (when the null hypothesis of equal adjusted means is rejected).

The main analysis of the primary endpoint will be performed using multiple imputation to account for missing data (Section 3.10.1.1; Section 3.10.2.7).

Supportive analyses will be performed on:

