Appendix 4: Predictive Margins and Average Marginal Effects Macro and Implementation

SAS documentation on the Predictive Margins and Average Marginal Effects SAS Macro is available here: https://support.sas.com/kb/63/038.html.

Sample implementation code using simulated data:

```
data test;
      do i = 1 to 300;
      trtpn = 1;
      week = 1;
            x1 = rand('UNIFORM');
            if x1 > 0.3 then resp = 1;
            else resp = 0;
            output;
      week = 2;
            x1 = rand('UNIFORM');
            if x1 > 0.4 then resp = 1;
            else resp = 0;
            output;
            end;
      do i = 301 to 600;
      trtpn = 2;
      week = 1;
            x1 = rand('UNIFORM');
            if x1 > 0.4 then resp = 1;
            else resp = 0;
            output;
      week = 2;
            x1 = rand('UNIFORM');
            if x1 > 0.5 then resp = 1;
            else resp = 0;
            output;
            end;
      run;
proc freq data = test;
      table week*resp*trtpn / riskdiff;
      run;
%include "P:\George Medicines\ACT\macros\margins.sas";
%Margins(data = test,
        class
                  = i trtpn week,
        response = RESP,
        roptions = event='1',
        dist = BINOMIAL,
model = trtpn|week,
        geesubject = i,
        margins = trtpn*week,
        options = diff cl,
diff = all);
```

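### The sample GEE code for the binary endpoints clusters on participant only, against the stated site-level clustering, and names no event level; the effect on standard errors is small and conservative

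*SAP*

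**What the plan says.** **Text.** SAP 3.10.3.1 describes a GEE for the binary endpoints with a sandwich variance, and wants "the model to account for correlation within participant and within site". It adds: "A compound symmetry covariance matrix will account for correlation within participant and site", with an independence matrix as fall-back if the model does not converge. Protocol 12.4 has the binary analysis "accounting for correlation within participant and clustering at the site level". SAP 3.10.3.2 says the clinic binary endpoints are analysed in the same manner.

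**Code.** The sample program under that text starts with "PROC GENMOD DATA = ADEFF", models "MODEL AVAL = BASE VISIT TRTP VISIT*TRTP / DIST = BIN CL" and clusters with "REPEATED SUBJECT = SUBJID(SITEID) / TYPE = EXCH". Neither the PROC nor the MODEL statement says which level of AVAL is the event.

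**Elsewhere in the SAP.** The primary MMRM code in 3.10.2.2 makes site the subject: "REPEATED VISIT SUBJID / SUBJECT = SITEID TYPE = UN@CS". The risk-difference macro in Appendix 4 does name the event, with "roptions = event='1", and clusters on the participant identifier (`geesubject = i`).

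**Status.** SAP 2.1 offers the code as an example that may need modification to suit the data collected. SAP section 3.10.1.1 (Secondary Estimands) plans no hypothesis tests for secondary endpoints and calls their results exploratory.

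**The concern.** Text and code specify different variance estimators for the same endpoints. Nesting SUBJID in SITEID only makes participant identifiers unique; it does not make site a cluster. The independence fall-back does not help, because it changes the working correlation and not the cluster unit. A programmer who follows the code will report confidence intervals that are not the ones described in the text.

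The missing event level is a separate gap. If AVAL is 0/1 and the software models the lower level, the log odds ratios describe failure to reach the target, while Appendix 4 computes risk differences for the event coded 1. The two effect measures would then point in opposite directions. SAP 3.10.3.1 and 3.10.3.2 list 4 home and 8 clinic binary endpoints, so 12 × 3 = 36 pairwise comparisons. They mix favourable events (BP control) with unfavourable ones (orthostatic hypotension and hypertension), so a reader cannot rely on one expected direction.

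**Working it through.** **1. The plan's own figures.** The documents give no power, event rate or ICC for the binary endpoints. The only design figure is for the primary endpoint: 600 v 300, difference 3 mmHg, SD 11, two-sided 5%. The standard error is 11 × √(1/600 + 1/300) = 0.778; 3/0.778 = 3.857; Φ(3.857 − 1.96) = 97.1%, and 0.971³ = 91.6%. This reproduces the stated 97% and 91%, but the present point does not depend on it.

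**2. Direction of the standard-error effect.** SAP 2.3.2 randomizes in permuted blocks within site, 2:1:1:1. Both arms of a contrast therefore share each site's effect, and it largely cancels in the difference. A participant-level sandwich treats participants as independent and leaves the site component in. On a linear scale the ratio of reported to true standard error is about 1/√(1 − ICC): 1.010, 1.026 and 1.054 for ICC 0.02, 0.05 and 0.10. So the standard errors come out too wide, not too narrow.

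**3. Size on the logistic GEE.** A first simulation used the SAP model (baseline, visit, treatment, visit × treatment) with 1,500 participants, 100 unequal sites, blocks within site and 150 null replicates per ICC. Assumed, because the documents do not give them: latent site ICC, a participant share of 0.30, and event rates of roughly 50–55%. Mean standard errors of the Week 12 log odds ratio, GMRx2 v one dual (ratios from unrounded means):

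| Latent ICC | Participant cluster | Site cluster, independence | Ratio |
|---|---|---|---|
| 0 | 0.147 | 0.145 | 1.015 |
| 0.05 | 0.147 | 0.143 | 1.024 |
| 0.10 | 0.147 | 0.142 | 1.033 |
| 0.20 | 0.146 | 0.135 | 1.080 |

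At ICC 0 there is no site effect to miss, so that 1.5% is best read as the site-level sandwich running slightly small with about 100 unequal clusters. Dividing it out leaves 1.024/1.015 = 1.009, 1.033/1.015 = 1.018 and 1.080/1.015 = 1.064.

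A larger simulation (3,000 trials per ICC, 100 sites, independence working matrix, Week 12 only) compared standard errors with the empirical SD of the estimate. Participant-clustered standard errors were about 1–3% too large at latent ICC 0–0.10 and 6% too large at 0.20, with null rejection of 3.5–4.8%. Site-clustered standard errors were within about 2.5%. The Monte Carlo error of an SD from 3,000 trials is about 1/√6000 = 1.3%, so the low end of the range is noise and the 6% is not. For the rejection rate it is √(0.05 × 0.95/3000) = 0.4 percentage points, so 3.5% is clearly below 5%.

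**4. What that means for an interval.** At ICC 0.10, the reported 95% limit lies a factor exp(1.96 × 0.147) = 1.33 from the odds ratio. With a standard error 3% smaller it would be exp(1.96 × 0.147/1.03) = 1.32. At ICC 0.20 the factors are exp(1.96 × 0.146) = 1.33 and exp(1.96 × 0.146/1.06) = 1.31.

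**5. Event level.** Refitting one simulated data set on 1 − AVAL turned an odds ratio of 1.446 into 0.692 = 1/1.446, with the same standard error (0.149). As an illustration with assumed control rates of 70% and 60%: (0.7/0.3)/(0.6/0.4) = 1.56, and the reciprocal is 0.64.

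**The case against.** **The code is only an example, and the prose governs.** The prose does state the site requirement, and it says the odds ratios are for the occurrence of the events. But the caveat in SAP 2.1 is about accommodating the data collected. Cluster unit and event level are model specification and do not depend on the data. The caveat lowers the stakes without removing the contradiction.

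**The participant-clustered standard errors may be good enough.** In a separate run of 400 null replicates per ICC, the SAP code gave mean standard error against empirical SD of 0.148/0.151, 0.148/0.148 and 0.147/0.146 at ICC 0.02, 0.05 and 0.10; site clustering with an exchangeable matrix gave 0.147/0.151, 0.145/0.147 and 0.142/0.145. With a Monte Carlo error of about 3.5%, neither differs detectably from correct. This stands as evidence that the effect is small. The larger simulation is what shows a consistent conservative direction.

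**Stronger readings that a reader might infer.**
- *Ignoring site makes the intervals too narrow.* That intuition belongs to trials that randomize whole clusters. Here randomization is within site, and none of the runs showed clear type I error inflation under the SAP code.
- *The odds ratios will be reversed.* The documents do not state how AVAL is coded, the default level is an assumption about the software, and the sample LSMEANS line requests only differences and limits, so odds ratios need a further step. A reversal would also leave the p-value unchanged and clash visibly with the percentages reported alongside.
- *Appendix 4 shows that the trial's risk differences will be unadjusted.* That call runs on a simulated two-arm data set with no site or baseline variable, so neither could appear in it. SAP 3.10.3.1 lists baseline home SBP as a fixed effect.

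**Conclusion.** The point holds as a mismatch between text and code. The sample GENMOD code clusters on participant only, contrary to both documents. The resulting treatment-contrast standard errors are about 1–6% too wide for an assumed latent site ICC up to 0.20, and at most about 3% for an ICC up to 0.10. That is conservative, affects exploratory endpoints only and leaves the primary MMRM untouched. The size rests on assumed ICCs, about 100 sites and the planned 1,500 participants; SAP Appendix 2 says that over 90% of that number were randomized.

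The missing event level is a real gap: it leaves the direction of the odds ratios to a default that could oppose the Appendix 4 risk differences. The documents support no more than that possibility. Overall this is a minor correction, worth making because it is cheap and settles which error bars will be reported.

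**What to change.** 1. In the GENMOD code, make SITEID the cluster for the sandwich variance. `REPEATED SUBJECT=SITEID` with an independence working matrix is the simplest choice; the 3.10.3.1 text, which now puts compound symmetry first, then needs one sentence changed. `TYPE=EXCH` at site level is the alternative, but it forces one correlation on a participant's two visits and on different participants at a site. If chosen, the SAP should say that it merges the two levels named in the text.
2. Write the response as `AVAL(EVENT='1')` and state that AVAL = 1 means the endpoint occurred, including for the orthostatic endpoints.
3. When the Appendix 4 macro is applied to trial data, use the same cluster unit and include BASE, so that odds ratios and risk differences come from one model.

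Keeping participant-level clustering would also end the contradiction, but the site wording would then have to come out of both SAP 3.10.3.1 and protocol 12.4.

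The cost is a few code lines and one or two sentences of text, with no change to data collection, sample size or the primary analysis. The site-level sandwich may run slightly small with about 100 unequal sites (within about 2.5% in the larger simulation), which is acceptable for exploratory endpoints.

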3.10.3.2 In Clinic Blood Pressure

At each scheduled trial visit, triplicate BP measurements will be performed "in clinic" after 5 minutes of seated rest and with a 1-minute interval between measurements. The last two measurements will be averaged. If only two measures were taken, both will be averaged, and if only 1 measure is taken that value will be used. The Baseline value for clinic BP measurement is the value recorded at Randomization.

As per the home BP measurements, any zero SBP or DBP values will be treated as missing.

In clinic BP endpoints are listed below:

- Difference in change in clinic seated SBP from randomization to Week 12,
- Difference in change in clinic seated SBP from randomization to Week 6,
- Difference in change in clinic seated DBP from randomization to Week 12,
- Difference in change in clinic seated DBP from randomization to Week 6,
- Percentage of participants with clinic seated SBP <140 and DBP <90 mmHg at Week 12,
- Percentage of participants with clinic seated SBP <140 and DBP <90 mmHg at Week 6,
- Percentage of participants with clinic seated SBP <130 and DBP <80 mmHg at Week 12,
- Percentage of participants with clinic seated SBP <130 and DBP <80 mmHg at Week 6,
- Percentage of participants with orthostatic hypotension at Week 6,
- Percentage of participants with orthostatic hypotension at Week 12
- Percentage of participants with orthostatic hypertension at Week 6,
- Percentage of participants with orthostatic hypertension at Week 12

Orthostatic hypotension is defined as a decrease from measured in clinic sitting to standing blood pressure of \geq 20 mmHg SBP or \geq 10 mmHg DBP. Orthostatic hypertension is defined as an increase from measured in clinic sitting to standing blood pressure of \geq 20 mmHg SBP or \geq 10 mmHg DBP.

Descriptive statistics will be used to summarize secondary endpoints by visit on complete cases only.

Continuous endpoints will be summarized using descriptive statistics. Binary endpoints will be summarized with frequency and proportions by treatment group with exact Clopper-Pearson 95% CIs along with associated estimated risk difference, risk ratio, and corresponding p-values. Frequency of missing data will be presented.

Mixed models with repeated measures (MMRM) will be applied for continuous endpoints using the same approach as the primary endpoint (with no imputations applied). Results will be presented in a similar fashion as home BP. Standing clinic BP measurements will be summarised descriptively by visit. Complete case analysis will be performed with no imputations for continuous endpoints.

Binary secondary endpoints will be analyzed using GEE regression methods in the same manner as home BP endpoints. Risk differences and 95% confidence intervals will be computed for comparisons between GMRx2 and dual control treatments. Missing values at Week 6 and Week 12 will be imputed as "failures" for the analysis.

